Appendix B. Reference Values/Toxicity Grades

Laboratory Values

Safety laboratory values below a distinct limit (eg. detection limit, documented as "< [limit]") will be substituted by half of the limit and values above a distinct limit (documented as "> [limit]") will be substituted by the limit itself for all analyses.

A Grade (based on CTC AE version 4.0 [v4.03: June 14, 2010]) will be assigned to each laboratory result as detailed in Table 2. Depending on the toxicity definition, the same result may be assigned to two grading for deviations towards higher or lower values. Values not meeting any of the criteria will be assigned a grade 0.

Table 2. Grading of Select Laboratory Parameters

Table 2. Grading of Select Laboratory Parameters							
Laboratory Abnormality [Unit]	Grade 1	Grade 2	Grade 3	Grade 4			
Decreased Lymphocytes [G/L]	0.8 - < LLN	0.5 - < 0.8	0.2 - < 0.5	< 0.2			
Decreased Neutrophils [G/L]	1.5 - < LLN	1.0 - < 1.5	0.5 - < 1.0	< 0.5			
Decreased Platelets [G/L]	75 - < LLN	50 - < 75	25 - < 50	< 25			
Decreased WBC [G/L]	3.0 - < LLN	2.0 - < 3.0	1.0 - < 2.0	< 1.0			
Decreased Hemoglobin [g/L]	100 - < LLN	80 - < 100	< 80	not defined			
Decreased Albumin [g/L]	30 - < LLN	20 - < 30	< 20	not defined			
Increased AST	> ULN – 3*ULN	> 3*ULN – 5*ULN	> 5*ULN – 20*ULN	> 20*ULN			
Increased ALT	> ULN – 3*ULN	> 3*ULN – 5*ULN	> 5*ULN – 20*ULN	> 20*ULN			
Increased Total Bilirubin	> ULN – 1.5*ULN	>1.5*ULN – 3*ULN	> 3*ULN – 10*ULN	> 10*ULN			
Increased Creatinine	>1 - 1.5 * BL or >ULN -	>1.5 - 3.0 * BL or >1.5 -	>3.0 * BL or >3.0 - 6.0 *	>6.0 * ULN			
	1.5 *ULN	3.0 * ULN	ULN				
Decreased Corrected Calcium [mmol/L]	2.0 - < LLN	1.75 - < 2.0	1.5 - < 1.75	< 1.5			
Increased Corrected Calcium [mmol/L]	>ULN - 2.9	>2.9 – 3.1	>3.1 – 3.4	>3.4			
Decreased Potassium [mmol/L]*	3.0 - < LLN	3.0 - < LLN; symptomatic; intervention indicated	2.5 - < 3.0	< 2.5			

Statistical Analysis Plan: 20140355

Date: 09 Jun 2017 Page 42

Laboratory Abnormality				
[Unit]	Grade 1	Grade 2	Grade 3	Grade 4
Increased Potassium [mmol/L]	5.5 - >ULN	>5.5 – 6.0	>6.0 – 7.0	>7.0
Decreased Sodium[mmol/L]	130- <lln< td="">not defined	120-<130	<120	</lln<>	not defined	120-<130	<120
Increased Sodium[mmol/L]	>ULN-150	>150-155	>155-160	>160
Decreased Phosphorus [mmol/L]	0.8 - <lln< td="">0.6 - <0.8	0.3 - <0.6	<0.3	</lln<>	0.6 - <0.8	0.3 - <0.6	<0.3
Increased Magnesium [mmol/L]	>ULN – 1.23	not defined	>1.23 – 3.30	>3.30
Decreased Magnesium [mmol/L]	0.5 - <lln< td="">0.4 - < 0.5	0.3 - <0.4	<0.3	</lln<>	0.4 - < 0.5	0.3 - <0.4	<0.3
Increased Uric Acid [mmol/L]^	>ULN – 0.59 without physiologic	not defined	>ULN – 0.59 with physiologic	>0.59
	consequences		consequences	

BL: baseline value, LLN: Lower limit of normal, ULN: Upper limit of normal Clinical criteria from CTCAE 4.0 grading were not considered in order to assign grades unless specified otherwise

^{*:} Details will be recorded on Potassium CTC Details CRF for central lab values and Chemistry (Local Lab) CRF for local lab values.

^{^:} Details will be recorded on Uric Acid CTC Details CRF for central lab values and Chemistry (Local Lab) CRF for local lab values.

Statistical Analysis Plan: 20140355

Date: 09 Jun 2017 Page 43

Appendix C. Patient-reported Outcome Forms/Instruments

The following sections describe the scoring algorithms used for both the QLQ-C30 and QLQ-MY20 questionnaires. Scoring procedures are similar for both questionnaires and can be found in the EORTC QLQ-C30 Scoring Manual, ver. 3 (Fayers et al. 2001) and Cocks et al (2007). All scale scores range from 0 to 100.

QLQ-C30 Scoring

For all scales, calculate the raw score (RS) of a scale using the mean of the item scores in the scale as follows:

$$RS = (S1 + S2 + ... + Sn) / n$$

where Si: i=1, ..., n, are the item scores and n is the number of items with valid scores, assuming the number of items with valid scores meets the minimum requirement as specified in Table 3 or this scale score will be assumed missing.

Use a linear transformation to standardize the raw score in order that scores will range from 0-100:

Global Health Status/QOL = {(RS-1)/range} * 100

Functional Scales = {1- (RS-1)/range} * 100

Symptom Scales = {(RS-1)/range} * 100

where range for each scale is defined in Table 3.

For the Global Health Status/QOL scale and functional scales in QLQ-C30 a higher score represents a better health state and for the symptom scores in QLQ-C30 a lower score represents a better health state.

QLQ-MY20 Scoring

For all scales, calculate the raw score (RS) of a scale using the mean of the item scores in the scale as follows:

$$RS = (S1 + S2 + ... + Sn) / n$$

where Si: i=1, ..., n, are the item scores and n is the number of items with valid scores, assuming the number of items with valid scores meets the minimum requirement as

Statistical Analysis Plan: 20140355

Date: 09 Jun 2017 Page 44

specified in Table 3 or this scale score will be assumed missing.

Use a linear transformation to standardize the raw score in order that scores will range from 0-100:

Disease Symptom Scale (DS) = $\{(RS - 1) / range\} * 100$

Side Effects of Treatment Scale (SE) = $\{(RS - 1) / range\} * 100$

Future Perspective Scale (FP) = $\{1 - (RS - 1) / range\} * 100$

Body Image (BI) = $\{1 - (RS - 1) / range\} * 100$

where range for each scale is defined in Table 3.

Table 3: QLQ-C30 and QLQ-MY20 Scales and Scoring Details

	Number	Item	Item	Minimum Not
01.0.020	of Items	Range ^a	Numbers	Missing
QLQ-C30 Global Health	2	6	20.20	1
	2	0	29,30	I
status/QOL				
Functional Scales				
Physical Functioning	5	3	1-5	3
Role Functioning	2		6,7	1
Emotional Functioning	4	3	21-24	2
Cognitive Functioning	2	3 3 3	20,25	1
Social Functioning	2	3	26,27	1
	_	J	20,21	1
Symptom Scales / Items				
Fatigue	3	3	10,12,18	2
Nausea/vomiting	2	3	14,15	1
Pain	2		9,19	1
Dyspnoea	1	3 3 3 3 3	8	N/A
Insomnia	1	3	11	N/A
Appetite Loss	1	3	13	N/A
Constipation	1	3	16	N/A
Diarrhoea	1	3	17	N/A
Financial Difficulties	1	3	28	N/A
QLQ-MY20				
Symptom Scales				
Disease Symptoms	6	3	31-36	3
Side Effects of	10	3	37-46	5
Treatment				
Functional Scales/Items				
Future Perspective	3	3	48-50	1
Body Image	1	3	47	N/A
Dody illiago	Į.		71	14// \

Statistical Analysis Plan: 20140355

Date: 09 Jun 2017 Page 45

^a Range is the difference between the maximum possible value of the Raw Score and the minimum possible value.

For the Disease Symptoms and the Side Effects of Treatment scales a high score represents a high level of symptomatology / problems (symptom scale). For Body Image and Future Perspective scales a high score represents a high level of functioning (functional scale), i.e. a better future perspective or body image.

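### SAP Appendix C lets the three-item QLQ-MY20 Future Perspective scale be scored from one answered item, while the other 11 multi-item scales in the same table need at least half their items

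*SAP*

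**What the plan says.** SAP Appendix C describes how the QLQ-C30 and QLQ-MY20 scales are scored. The raw score is the mean of the valid items, then rescaled to 0 to 100. It is calculated only if the number of valid items "meets the minimum requirement as specified in Table 3 or this scale score will be assumed missing". That sentence stands under QLQ-C30 scoring, and the same rule is repeated under QLQ-MY20 scoring. The Table 3 meant is the one inside Appendix C, not the stopping-boundary table of SAP Section 8.

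The columns are number of items, item range, item numbers and the minimum number not missing. The row at issue, for the QLQ-MY20 scale "Future Perspective", reads "Future Perspective 3 3 48-50 1": three items, range 3, items 48 to 50, minimum 1. The only other three-item scale reads "Fatigue 3 3 10,12,18 2", so its minimum is 2.

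The appendix introduces the scoring procedures as similar for the two questionnaires. It refers to the QLQ-C30 scoring manual and to a separate QLQ-MY20 publication. It says nothing about Future Perspective being an exception.

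SAP Section 9.3 sends missing-data rules for endpoints to Sections 6 and 10. The patient-reported outcome text in Section 10.5.3 has no item-level rule, so Table 3 of Appendix C is the only one.

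**The concern.** Two scales of equal length, in one table and under one scoring formula, have different missing-data thresholds. A program written from the SAP would keep a Future Perspective score that rests on one third of its items and would discard a Fatigue score with the same pattern of missing items. Both scales then go into the by-visit, by-arm summaries of scores and changes from baseline in SAP Section 10.5.3.

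What is at stake is consistent handling of partly completed forms, and whether a reader can tell if the looser threshold was intended. If the entry is a slip and is corrected only after the data have been seen, the correction invites the question of why it was made then.

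**Working it through.** **Inputs.** All come from Table 3 of SAP Appendix C. Write n for the number of items and m for the stated minimum.

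**Step 1: look for the rule behind the minima.** The natural candidate is at least half the items, m = n/2 rounded up.

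| Scale | n | stated m | m/n | n/2 rounded up | agrees |
|---|---|---|---|---|---|
| Global Health, Role, Cognitive, Social, Nausea/vomiting, Pain (six scales) | 2 | 1 | 50% | 1 | yes, all six |
| Fatigue | 3 | 2 | 67% | 2 | yes |
| Emotional Functioning | 4 | 2 | 50% | 2 | yes |
| Physical Functioning | 5 | 3 | 60% | 3 | yes |
| Disease Symptoms (QLQ-MY20) | 6 | 3 | 50% | 3 | yes |
| Side Effects of Treatment (QLQ-MY20) | 10 | 5 | 50% | 5 | yes |
| Future Perspective (QLQ-MY20) | 3 | 1 | 33% | 2 | **no** |

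The rows for the longer scales read "Emotional Functioning 4 3 21-24 2", "Physical Functioning 5 3 1-5 3", "Disease Symptoms 6 3 31-36 3" and "Side Effects of 10 3 37-46 5". The rule reproduces 11 of the 12 multi-item entries; Future Perspective is the exception. The seven single-item scales are marked not applicable and do not enter the comparison.

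**Step 2: can any rule based on item count fit all 12?** No. Fatigue and Future Perspective both have n = 3, with minima of 2 and 1. Rounding n/2 down would give 1 for n = 3 and so fit Future Perspective, but it would then miss Fatigue (1 against 2) and Physical Functioning (2 against 3).

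**Step 3: what does a one-item score look like?** For Future Perspective the score is {1 − (RS − 1)/3} × 100, where RS is the mean of the valid items.

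- One item scored 1, 2, 3 or 4 gives 100, 66.7, 33.3 or 0.
- Answers 1, 4, 4 give RS = 9/3 = 3 and a score of (1 − 2/3) × 100 = 33.3.
- If only the first of those items is answered, RS = 1 and the score is 100.
- If only one of the items scored 4 is answered, the score is 0.

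**Step 4: how many forms are affected?** Only those with exactly one of items 48 to 50 answered. With two or three answered, a minimum of 1 and a minimum of 2 give the same score; with none answered, both give missing. The documents state no item-missingness rate. Assuming that each item is missing independently with probability p, the share is 3(1 − p)p²:

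| Assumed p | 3(1 − p)p² | Share of forms |
|---|---|---|
| 2% | 3 × 0.98 × 0.0004 | 0.1% |
| 5% | 3 × 0.95 × 0.0025 | 0.7% |
| 10% | 3 × 0.90 × 0.01 | 2.7% |
| 20% | 3 × 0.80 × 0.04 | 9.6% |

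**The case against.** The strongest reply is that the SAP never states an at-least-half rule. It makes the table itself the rule and lists minima one scale at a time, so a scale-specific value is possible by design. On the SAP's own terms a score from one item of three is valid. This stands. A reader might infer that such scores ought to be missing, or that the SAP breaks a stated rule. The documents do not support either reading, because the half rule is only a pattern seen in the other 11 rows.

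A second reply is that the appendix cites a separate source for the QLQ-MY20, and that similar procedures need not be identical. The other two multi-item QLQ-MY20 scales have 6 and 10 items. Even counts cannot show whether the module rounds a half up or down, so the QLQ-MY20 rows alone do not exclude an intended minimum of 1. This also stands, and it makes the fix conditional.

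Third, scores resting on one item are not peculiar to this scale. The table accepts them for seven single-item scales, and for the two-item scales when one item is answered. That is so. Coarse scores are therefore not the defect; the unequal treatment of two scales of the same length is.

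Fourth, the text of this table was read from a PDF and some neighbouring rows are garbled. The Future Perspective row reads cleanly in every column, but the point turns on one digit and it should be checked on the page.

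Finally, the consequence is slight. The scale is exploratory. SAP Section 10.5.3 summarises subscales descriptively and, for between-arm comparison, names only Global Health Status as its example. The same threshold applies to both arms, and Protocol Section 10.7 has the study coordinator sign off that questionnaires were completed. All of this is accepted; none of it explains why Fatigue needs 2 and Future Perspective 1.

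**Conclusion.** The point holds as an unexplained inconsistency in an operative missing-data convention. It is not an arithmetic error. One of the 12 multi-item scales has a minimum below half its items, and the one other scale of the same length is treated more strictly.

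The size is small: an exploratory subscale, only forms with exactly one of three items answered, and no effect on PFS, ORR, OS, alpha or sample size. The shares of 0.1% to 9.6% rest on assumed independent item missingness of 2% to 20% and are illustrative.

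Two things remain open: whether the printed digit is 1, and whether the cited QLQ-MY20 source specifies that minimum. A reader might also infer a biased treatment comparison. Nothing in the documents points to partial completion of these items differing between arms, so that does not follow.

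**What to change.** Confirm the Future Perspective entry on the original page of Table 3 in SAP Appendix C. Then change the minimum from 1 to 2, which brings it into line with Fatigue and the rest of the table. If the cited QLQ-MY20 scoring source does specify 1, keep it and add a footnote naming that source, so that the difference from Fatigue is seen to be intended.

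A sentence stating the general rule, at least half the items unless footnoted, would remove the need to infer it. The cost is one digit or one footnote, with no new data; it should be done before the patient-reported outcome scores are derived.
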